8.3 STUDY OUTCOME MEASURES

8.3.1 Primary endpoint:

- The ability of the JSI to correctly insert a stent into the ureter of a suitable participant as determined by post-stenting KUB plain X-ray.
 - Timepoint: Immediately post-stent insertion with KUB Xray
 - Measure: Investigator's assessment of position of superior part of stent within kidney collecting system on KUB plain X-ray performed after stent insertion (Yes/No/Unsure)
 - If "Unsure"- proceed to renal ultrasound to confirm.
 - If "No" or still "Unsure" then proceed to standard stent insertion in operating room

8.3.2 Secondary endpoints:

- The mechanical reliability of the JSI to perform its function correctly as determined by the treating doctor as noted on a global doctor satisfaction score.
 - Timepoint: Immediately post-device usage
 - Measure: Rating of device reliability, i.e. correct mechanical function to work as intended on global doctor satisfaction score.
- The clinical safety of the JSI.
 - Timepoint: Immediately post-intervention commencement through to final follow up visit.
 - Measure: Assessed using reported adverse events, device deficiencies and participant questionnaire.
- Time taken to insert the ureteric stent using JSI (measures stent insertion procedure time only, workflow data assesses overall workflow and will be assessed separately).
 - Timepoint: Immediately post-intervention commencement.
 - Measure: Use of stopwatch or calculated from start and end times and recorded on a

case report form.

- Feasibility- evaluation of participant recruitment rate.
 - Timepoint- At study completion. To be completed within 6 months of study commencement.
 - Measure: A log will be kept of all participants invited to the study and if applicable, their reasons for refusal noted. Feasibility will be assessed using recruitment/withdrawal data and an audit of study enrolment and withdrawal logs.
- Participant experience and satisfaction with the JSI.
 - Timepoint: Prior to stent insertion (within 2 hours), Post stent insertion (within 1 hour), and at follow up visit for definitive stone management surgery (within 14-21 days)
 - Measure: Participants will receive a Patient Satisfaction Questionnaire regarding their experience of ureteric stent insertion with the JiffyStent Inserter.
- User satisfaction for urological doctor/study researcher.
 - Timepoint- Immediately after stent-insertion.

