9.2 Schedule of Assessment

| Assessments | Screening (Day -7 to Day 1) | Procedure (Day 1) | Follow Up Visit (14 to 21 Days Post Tx) |
|------------------------------|--------------------------------|----------------------|--|
| Informed consent | X | | |
| Inclusion/Exclusion Criteria | X | | |
| Medical History | X | | |
| Demographics | X | | |
| CT Scan / MRI | X ^a | | |
| KUB X-Ray | | X ^b | |
| Renal Ultrasound | | (X) ^c | |
| User Questionnaire | | X ^d | |
| Participant Questionnaire | | X ^e | X |
| Device Deficiencies | | X | |
| Adverse Events | X | X | X |
| Concomitant Medications | X | X | X |
| Stone Management | | | X ^f |

- a. Prior imaging may be collected up to 30 days prior to treatment
- b. Performed after stent insertion for confirmation of position of the stent.
- c. If unable to confirm stent positioning via X-Ray, then proceed to perform renal ultrasound
- d. Performed ‘Immediately after stent-insertion’
- e. Performed ‘Prior Insertion’ and ‘Post Insertion’
- f. As per standard practice

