10.3 Ethical considerations of consent

The ethical considerations related to consent will be minimal in this project. This is primarily because eligible participants all require a ureteric stent. This stent can be inserted with the JSI or by the standard procedure in an operating room. Therefore, the consent is no different to the usual consent process for having a stent inserted apart from the fact that this is a new technique with a novel medical device. Only fully informed participant who can understand English or have it carefully explained to them by an interpreter we be eligible to participate in the study. There are no cultural issues that may affect this consent process.

10.4 Management of participant's expectation of the perceived benefit of participating in the research

Participants expectations will be managed by a careful and adequate fully informed consent process. This will involve explaining to the participant that the JSI is currently an experimental medical device. They will be informed that the insertion of a correctly placed stent is identical to that achieved by the standard procedure in an operating room. It will also be explained that we expect there to be a 5 to 10% failure rate that will require going to theatre for insertion of a stent via the standard procedure. It will also be carefully explained that there is a risk of incorrect placement and potential damage to the ureter that maybe more easily recognised in the operating room with the benefit of real-time image intensifier X-ray.

10.5 Ethical considerations relating to the collection and/or use of the information/data in this project

Participants will be allocated a unique study number. The site research coordinator will compile an enrolment log, including the participant's name, date of birth, hospital identification number, unique study number and date and time of procedure. Subsequent data will be identified by the unique study number only. The enrolment log and study data will be kept separately. Study data will be entered into a password protected REDCap database managed by the principal investigator. No identifying data will be entered into the database.

Similarly, hard copies of study data collected on paper source worksheets will be stored separately in the locked office of the principal investigator. Only the PI and research team will have access to this information, and they will not disclose this information to any other person or entity.

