11.2.1 Clinical risks

| Hazard | Risk | Mitigation and residual risk |
|--|--|--|
| 
Guidewire perforates the ureter which is unrecognised while using the device.
 
Probability: Likely Severity: Serious See Appendix A for scores at bottom of sheet
 | 
The stent will be inserted outside of the ureter. Consequences: Obstruction not relieved Pain not relieved Increased risk of infection Risk of long-term ureteric stricture The risk of a 1.67 millimetre diameter hole in the ureter is minimal. There is a small risk of long-term ureteric stricture which may be related to the perforation or more likely the impacted stone causing inflammation and scarring at this point in the ureter. Despite optimal conditions, this can sometimes happen during the standard procedure in an operating room but may be recognised with the benefit of the in-theatre imaging intensifier X ray machine.
 | 
A post-stent insertion KUB X-ray will be performed to confirm position of stent. Patients with incorrectly placed stents will be taken to the operating room for removal of the stent and insertion of a new stent under image intensifier guidance.
 |
| 
Guidewire does a U-turn in the ureter
 
Probability: Possible Severity: minor
 | 
The stent will be in the ureter below the level of obstruction. Consequences: Obstruction not relieved Pain not relieved This will cause no permanent harm to the participant.
 | 
A post-stent insertion KUB X-ray will be performed to confirm position of stent. This risk can be mitigated by careful participant selection as per our indications of a stone <1cm in size and in stones that are not impacted. Participants with incorrectly placed stents will be taken to the operating room for removal of the stent and insertion of a new stent under image intensifier guidance.
 |

| | | |
|---|--|---|

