11.2.2 Device Mechanical Risks

| Hazard | Risk | Mitigation and residual risk |
|---|---|---|
| Device failure or Spools get jammed and fail to work correctly- no stent inserted Probability: Possible Severity: negligible | Stent is unable to be inserted. Minimal harm to participant. | Quality design and manufacture processes and strict adherence to best practice QMS. Procedure abandoned and take to theatre as per standard procedure for stent insertion. |
| Spools get jammed and fail to work correctly- partial stent insertion Probability: Possible Severity: minor | Procedure not completed successfully. Stent half hanging out and may be across urinary sphincter leading to temporary incontinence. | Quality design and manufacture processes and strict adherence to best practice QMS. Procedure abandoned and take to theatre as per standard procedure for removal of stent and insertion of new stent. |

| | | |
|---|---|--|
| 
Incorrect guidewire length set-too long
 
Probability: Possible Severity: serious
 | 
Guidewire inserts too far. Usually, guidewire has floppy end that will curl up in collecting system of kidney. Stent still inserted correctly. Very rarely, guidewire will pierce top of kidney collecting system and stent may be inserted outside of kidney.
 | 
Device has a failproof stop so that the guidewire cannot be inserted more than 33cm. We will use a guidewire with a 3cm floppy tip that will curl if it hits end of collecting system. Device has variable length settings for shorter ureters. These will be related to the height of participant and clearly marked on the device. instructional online video will provide education around ureteric length determination. In the case of no length being set, the guard wire will be limited at 33 centimetres which will be safe in nearly all instances. Post procedure KUB X-ray will confirm correct position of upper end of stent within the kidney collecting system.
 |

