14.3 Analysis of the primary endpoint

Correct placement of the stent into the ureter as visualised on KUB plain x-ray post procedure.

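### A 'Yes' on one post-insertion plain X-ray is final for the primary endpoint, and the planned surgery at 14-21 days is not used to check it

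*Protocol*

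**What the plan says.** Section 8.3.1 defines the primary measure as the investigator's Yes/No/Unsure judgement of "position of superior part of stent within kidney collecting system on KUB plain X-ray performed after stent insertion", with "Timepoint: Immediately post-stent insertion with KUB Xray". Ultrasound follows only an 'Unsure'. A 'No', or an 'Unsure' that ultrasound does not settle, goes to standard insertion in theatre. The schedule in Section 9.2 agrees: the KUB film appears on the procedure day only, and its footnote reads "If unable to confirm stent positioning via X-Ray, then proceed to perform renal ultrasound". Section 14.3 describes the primary analysis as "Correct placement of the stent into the ureter as visualised on KUB plain x-ray post procedure".

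The risk tables name the placement failures that this endpoint has to detect. Section 11.2.1 lists "Guidewire perforates the ureter which is unrecognised while using the device", rates it 'Likely' and 'Serious', and gives a stent lying outside the ureter as the result. Appendix A sets 'Likely' at 10%. The mitigation is the post-insertion KUB. Section 11.2.2 adds: "Very rarely, guidewire will pierce top of kidney collecting system and stent may be inserted outside of kidney". Section 10.4 says participants will be told of a risk of misplacement and of "potential damage to the ureter that maybe more easily recognised in the operating room".

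Section 9.9 places definitive stone surgery at the 14-21 day visit. The data lists in Section 13.5 contain no item for stent position at that time, and no section links what surgery finds to the primary endpoint.

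**The concern.** For the perforation hazard, one film does two jobs: it is the only detection step named, and it is the endpoint. If the film is read 'Yes' while the stent lies outside the ureter, nothing in the plan can correct the primary result. Yet the participant is due for an operation two to three weeks later at which the stent's position may become apparent.

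The reading is made by the investigator in an unblinded single-arm study (Section 14.2). The SDMC reviews efficacy, reliability and safety after the first five participants before enrolment continues (Section 15.8), and the synopsis says a positive outcome will lead to a pivotal trial. With at most 15 participants, each misread case moves the success rate by 1/15 = 6.7 points. If position at surgery is not collected, no later analysis plan can recover it.

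**Working it through.** **The plan's own figure.** Section 14.1 gives no sample size calculation, target or power, so there is nothing to reproduce.

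**Inputs**
- Hazard rate before the X-ray: p = 0.10 ('Likely', Section 11.2.1 and Appendix A).
- Sample size: n = 15 in total, of whom up to 10 are in Group 2 (Section 9.1).
- Interval for categorical outcomes: two-sided exact 97% (Section 14.1).
- f, the chance that the KUB is read 'Yes' when the stent is outside the ureter. The protocol does not give it. Assumed range: 0 to 100%.
- Assumptions: participants are independent, and p and f are the same in both groups.

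**Step 1: hazard before the X-ray.** Expected perforations in 15 = 15 × 0.10 = 1.5. P(at least one) = 1 − 0.9^15 = 79.4%. For n = 10: 1.0 expected and 1 − 0.9^10 = 65.1%. These are not false-success rates.

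**Step 2: false successes.** The reported rate exceeds the true rate by p × f = 10 points × f. P(at least one false success) = 1 − (1 − 0.10f)^n.

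| f | Bias (points) | Expected in 15 | P(≥1), n = 15 | P(≥1), n = 10 |
|---|---|---|---|---|
| 0% | 0 | 0 | 0% | 0% |
| 10% | 1.0 | 0.15 | 14.0% | 9.6% |
| 25% | 2.5 | 0.375 | 31.6% | 22.4% |
| 50% | 5.0 | 0.75 | 53.7% | 40.1% |
| 100% | 10.0 | 1.5 | 79.4% | 65.1% |

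The n = 10 column is relevant because Group 1 is treated in the operating room, where recognition may be easier.

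**Step 3: effect of one misread case** (Clopper-Pearson, 97%). When all succeed, the lower limit is 0.015^(1/n).
- All participants: 15/15 gives 75.6-100%; 14/15 gives 65.3-99.9%.
- Group 2: 10/10 gives 65.7-100%; 9/10 gives 52.1-99.8%.

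One case lowers the lower limit by 75.6 − 65.3 = 10.3 points overall and by 65.7 − 52.1 = 13.6 points in Group 2.

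**The case against.** The strongest reply is that nothing in the protocol shows the KUB to be unreliable. Sections 11.2.1 and 11.2.2 rely on it to confirm position. The endpoint also requires the upper end to lie in the collecting system, so many misplaced stents may be read 'No'. The remarks about theatre imaging compare settings and do not say that the film fails. This stands: f could be close to zero, and the point is that the plan cannot find out.

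A reader might infer that 10% of stents, about 1.5 in 15, will be counted wrongly as successes. The text does not support that. The rating covers perforation unnoticed during device use, before the film is taken. It is also a risk-category value, and this one hazard at 10% would equal the top of the 5-10% failure rate given to participants in Section 10.4. The stent outside the kidney is described as very rare.

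A reader might infer that the error can run only towards success. That is not shown either. A 'No' goes to theatre without ultrasound, and nothing re-scores a false 'No'.

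A reader might infer that misplacement is hidden from the safety result. It is not. Safety runs to the final visit (Section 8.3.2), adverse events are recorded at the visit that includes surgery (Section 9.9), and none is exempt from reporting (Section 15.2).

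Finally, Section 14.3 mentions only the KUB, and one might read that as excluding ultrasound-confirmed stents. Since Section 8.3.1 uses ultrasound to settle an 'Unsure', success is the natural reading, and this is mainly a matter of wording.

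**Conclusion.** The point holds as a gap in verification. A 'Yes' on one investigator-read film is final, the same film is the only detection step named for a stent outside the ureter, and the planned surgery does not feed back to the endpoint. Adverse event collection could still capture the event, but the primary result would not change.

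The possible upward bias is 10 points × f, between 0 and 10 points. It rests on the protocol's 10% category value and on a miss rate that the documents do not give. They support neither a specific false-success rate nor a claim that the endpoint is invalid. For a descriptive first-in-human pilot this is an inexpensive improvement worth making: it lets the trial test its own primary result, in a sample where one case takes about 10 points off the lower confidence limit.

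**What to change.** 1. **Sections 9.2 and 13.5:** add a CRF item completed at the standard-care stone surgery or stent removal, or from any CT done for care. Record stent position as in the ureter and collecting system, outside, migrated, or not assessed, and note any sign of perforation.
2. **Sections 8.3.1 and 14.3:** keep the Day 1 result as primary. Add one sensitivity row that re-scores a Day 1 reading contradicted by later direct evidence of the original placement, in either direction where such evidence exists. Code migration separately and do not treat it as original misplacement.
3. **Section 14.3:** align it with Section 8.3.1 by stating that, where ultrasound is done after an 'Unsure', its result sets the endpoint value.

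The cost is one CRF item, one table row and a few sentences. No extra imaging, procedure or change in clinical management is needed. The success figure in the sensitivity row may fall slightly, some participants will be 'not assessed', and separating migration from original misplacement will need a brief judgement by the assessor.

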5 BACKGROUND

5.1 Lay Summary

A common presentation to the emergency department is a patient in excruciating pain from a kidney stone obstructing the ureter and kidney. Many of these patients will require a ureteric stent to relieve the obstruction and their pain. The current best treatment is to admit these patients to the operating room and insert a ureteric stent with the patient under general anaesthetic. This process can take 24 hours or more. The JiffyStent Inserter (JSI) is an innovative single use medical device that allows the Urologist or Emergency Department Physician to insert a ureteric stent while the patient is in the emergency room. This is a proof-of-concept study to show that the JSI works as desired by correctly inserting a stent into the ureters of participants, initially under controlled conditions in the operating room, and then in the emergency department. It is anticipated that use of the device will take 3-5 mins. If a stent cannot be inserted with the JSI after the first attempt, then a stent will be inserted in the operating room by the standard procedure. The outcome of every JSI and the success of the stent insertion will be recorded by the trial team by medical record review and discussion with the treating doctor. The study will involve up to 15 participants under controlled conditions. Of the 15 total participants, five (5) will be individuals who require a stent as a standard part of their urological procedure and 5-10 participants will be individuals who present to the emergency room with acute renal colic from a kidney stone and require a ureteric stent insertion. A successful outcome will lead to a pivotal multicentre clinical trial necessary for regulatory approval thereby making the JiffyStent Inserter available for widespread use.

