6.8 Device traceability

Access to investigational devices will be controlled and the investigational devices will be used only in the clinical investigation and according to the clinical investigation plan. The sponsor will keep records to document the physical location of all investigational devices from shipment of investigational devices to the investigation sites until return or disposal. The sponsor shall have instructions in place and make packaging materials available, if applicable, for the safe return or disposal of investigational devices, including potentially hazardous devices. The devices will be identified by a serial number and expiry date. One device will be used per participant.

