6.9 Investigational device and comparator

One (1) JiffyStent Inserter device will be used per participant. There will be no comparator device.

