| 
LED lights fail to illuminate
 
Probability: Possible Severity: minor
 | 
Procedure cannot be started or completed. Minimal harm to participant. Financial risk with single use device.
 | 
Quality design and manufacture principles of board and WIFI components. Extensive mechanical, electrical and aging/transport testing. Device can be removed without injury to participant. If stent is partially deployed, it can be removed or if in urethra then the only downside is temporary incontinence. Participant taken to theatre for stent removal and insertion of new stent.
 |
| 
Camera does not work.
 
Probability: Possible Severity: minor
 | 
Procedure cannot be started or completed. No to minimal harm to participant. Financial risk with single use device.
 | 
Quality design and manufacture principles of board and WIFI components. Extensive mechanical, electrical and aging/transport testing. Device can be removed without injury to participant. If stent is partially deployed, it can be removed or if in urethra then the only downside is temporary incontinence. Participant taken to theatre for stent removal and insertion of new stent.
 |

| | | |
|--|--|--|
| | | Use new device or take to operating room as per standard procedure. |
| Electronic board faults Probability: Possible Severity: minor | Procedure cannot be started or completed. No to minimal harm to participant. Financial risk with single use device. | Use new device or take to operating room as per standard procedure. |
| Battery faults Probability: Possible Severity: minor | Procedure cannot be started or completed. No to minimal harm to participant. Financial risk with single use device. | Use new device or take to operating room as per standard procedure. |
| Privacy of Wi-Fi connection. Probability: Unlikely Severity: serious | Participant's face and or genitals may be seen before inserting proboscis. Minimal risk of identification or harm once inside bladder. | Extremely private and secure connection that cannot be viewed by anyone else. De-identified so minimal harm of view of inside of bladder. No data is transmitted. Video is only real-time and not recorded or saved. Only one connection can be made to Wi-Fi. |

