13.5.3 Investigator Experience

- Rate each of the following (1-5) upon ease of
 - Opening of sterile package
 - Setting of estimated ureter length on guidewire spool using adjustable pin
 - Loading of ureteric stent onto guidewire and into ready position (including use of provided pusher)
 - Winding action of guidewire spool
 - Connection of JSI to Smart device utilising QR codes
 - Visual/connection quality of Smart device video feed
 - Connection of irrigation fluids
 - Ergonomics of JSI insertion into urethra
 - Insertion of JSI into urethra
 - Aligning guidewire with desired ureteric orifice
 - Advancement of guidewire & stent along ureter to desired position
 - Ability to maintain visualisation of ureteric orifice during GW advancement & retraction
 - Disconnection of stent
 - Removal of JSI from urethra

- Analgesia/sedation utilised.
- Perceived participant tolerance of procedure (very poorly, poorly, tolerated, well tolerated)
- Difficulties encountered.
- Complications
- Overall rating of JSI procedure
- Other comments

13.5.4 *Participant experience*

- Measurement of pain before during and after treatment
- Rate of experience and satisfaction
- Other comments

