14.5 Analysis Populations

Analysis of the primary objective will be conducted using the intent-to-treat sample including all participants treated with the JSI.

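### Mechanical reliability is measured only by an operator's rating, and the plan conflicts on replacing a faulty device, so neither the reliability nor the success result need show a malfunction

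*Protocol*

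**What the plan says.** **Reliability.** The synopsis lists reliable working of the device first among the things the study will establish, and reliability is the first attribute named in the aim (Protocol 8.1). The corresponding secondary endpoint in 8.3.2 is judged by the treating doctor. Its measure is "Rating of device reliability, i.e. correct mechanical function to work as intended on global doctor satisfaction score". Neither a malfunction nor a count of malfunctions is defined there. The investigator variables in 13.5.3 are 1–5 ease ratings for the steps of the procedure, difficulties encountered, complications and "Overall rating of JSI procedure". User satisfaction is a separate secondary endpoint.

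**Objective device data.** Deficiencies are scheduled for the procedure day (9.2), defined to include malfunctions (15.1.4), and must all be documented (15.5.2). In 8.3.2 they appear in the measure of clinical safety. The device serial number is a procedure variable (13.5.2) and part of the accountability log (Section 17).

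**Number of devices per participant.** Section 6.9 says "One (1) JiffyStent Inserter device will be used per participant", and 6.8 says "One device will be used per participant". The lay summary (5.1) says "If a stent cannot be inserted with the JSI after the first attempt, then a stent will be inserted in the operating room". In 11.2.3, the rows for camera failure, electronic board faults and battery faults say "Use new device or take to operating room as per standard procedure".

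**Primary endpoint.** There is one Yes/No/Unsure reading of stent position per participant (8.3.1), analysed in the "intent-to-treat sample including all participants treated with the JSI" (14.5). Neither passage says which device must have placed the stent.

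**The concern.** A first-in-human device study should be able to say how many devices were opened and how many failed to work. A rating on a satisfaction score cannot supply that. An operator may rate a procedure well because it ended well, even if one device had to be discarded on the way.

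The conflict over replacement carries the problem into the primary result. If the three fault rows are followed, a participant whose first device faults can receive a correctly placed stent from a second one. The X-ray reads Yes and the participant is a success. The reliability rating may be favourable too. The results are meant to lead to a pivotal trial, whose design needs the malfunction rate and the first-device success rate.

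**Working it through.** The plan states no power, threshold or reliability figure, so there is nothing of its own to reproduce. The check compares the text first and then sizes the effect.

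**1. Which result would show a malfunction?** Take a participant whose first device has a camera fault and whose stent is then placed correctly by a second device.

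| Result | What is recorded | Malfunction visible? |
|---|---|---|
| Primary endpoint (8.3.1) | Yes, one answer per participant | No |
| Mechanical reliability (8.3.2) | Doctor's rating | Not as a count |
| Clinical safety (8.3.2) | Device deficiency | Yes |
| Accountability (Section 17) | Two devices logged against one participant | Yes, by inspection of the log |

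**2. Is the second device permitted?** Sections 6.8 and 6.9 say one device per participant, and 5.1 sends the participant to the operating room after a failed first attempt. The three rows in 11.2.3 offer a new device or theatre, and the camera row also says that the participant is taken to theatre. These statements cannot all be followed as written.

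**3. Effect of one swap.** The intervals are Clopper–Pearson at the two-sided 97% level that 14.1 gives for categorical variables.

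| n | Any-device success | First-device success |
|---|---|---|
| 15 | 15/15 = 100% (75.6 to 100) | 14/15 = 93.3% (65.3 to 99.9) |
| 10 | 10/10 = 100% (65.7 to 100) | 9/10 = 90.0% (52.1 to 99.8) |

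The difference at n = 15 is 1/15 = 6.7 percentage points. For scale, 10.4 expects 5 to 10% of insertions to fail and go to theatre. At device level the same case gives 16 devices opened and 15 without a fault: 15/16 = 93.8%.

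**4. How likely is at least one such fault?** Inputs:
- Three rows in 11.2.3 that allow a new device, each scored Possible.
- Possible = 1% (Appendix A, Risk Score Matrix).
- n = 10 to 15, from five participants in Group 1 plus 5–10 in Group 2 (9.1).
- Independence between rows and between participants, which is an assumption of this review.

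Per participant: 1 − 0.99³ = 2.97%.
n = 10: 1 − 0.99³⁰ = 26.0%.
n = 15: 1 − 0.99⁴⁵ = 36.4%.

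These are chances of a fault. The chance of a swap is no larger, and is smaller to the extent that theatre is chosen instead.

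**The case against.** **The failures are recorded.** This is the strongest reply, and it stands. Section 5.1 promises a record of the outcome of every inserter, separate from stent success. Deficiencies are documented and feed the safety endpoint, serial numbers are logged, and the safety committee reviews reliability after the first five participants (15.8). A reader might infer that malfunctions could vanish from the trial. The documents do not support that. What is missing is their appearance in the two results that bear on reliability and success.

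**The rating is of mechanical function, and the form may contain more.** The measure does refer to correct function, and several ease ratings in 13.5.3 track device steps. They grade ease, however, and do not count passes and failures. The questionnaire itself is not shown, so it cannot be said that it lacks a reliability item. The point rests on the measure fixed in 8.3.2, not on the form.

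**The conflict is narrow.** This is also true. It lies in three rows of a risk table that covers general product use as well, and theatre is offered in each. Those rows still describe a route that 6.8 and 6.9 exclude, and the primary endpoint has no rule for it.

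**The size could be overstated.** A reader might add the smart-device battery row in 11.2.3 as a fourth hazard and reach 1 − 0.99⁶⁰ = 45%. There, the device to be replaced is plausibly the phone or tablet, so the row is not counted. A reader might also picture several rescued faults. At the plan's own 1% per row, three or more affected participants among 15 has a probability of about 0.9%, so one swap is the fair illustration.

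**Conclusion.** The point holds in a limited form. As written, the reliability endpoint gives no malfunction rate, although the data for one are already collected. The device-use passages conflict, and a stent placed by a second device could be scored as a primary success. The malfunction would be found under safety, but not in the reliability or success result. One swap in 15 is worth 6.7 percentage points.

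The 26% and 36% figures rest on the plan's 1% scores, on independence, and on counting only the three clear rows; they are chances of a fault, not of a swap. The study is descriptive with no success threshold, so no formal decision turns on this. What is affected is how a lead objective is measured and what the pivotal trial can take from it.

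**What to change.** 1. In 8.3.2, define mechanical reliability as the number of devices opened without a recorded deficiency that prevented intended function, divided by all devices opened, with an exact confidence interval. Keep the doctor's rating under user satisfaction.
2. In 8.3.1, score the primary endpoint on the first device opened for each participant. Report any placement by a second device separately.
3. The sponsor must reconcile 5.1, 6.8 and 6.9 with the three fault rows in 11.2.3. This review does not say which rule should apply; items 1 and 2 work under either.

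The cost is endpoint wording. The deficiency records, serial numbers and accountability log are already planned. The reported figures may come out less favourable than under the present wording.
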